4.4.1.2.2 Intensity

Intensity will be derived according to the following classification: None, Grade 1, Grade 2, Grade 3, or Missing

If the unsolicited AE is measurable and its preferred term is part of the list of solicited reactions, then the measurement is derived based upon and following the same rule of the intensity scales defined in the protocol for that measurable injection site or systemic reaction. Note the intensity could be considered as "None" (not a reaction) in the analysis despite being considered a reaction by the investigator .

Intensity for the other unsolicited AEs will correspond to the value reported in the CRF.

The maximum intensity corresponds to the highest intensity for a unique term.

4.4.1.2.3 Last Vaccination

Last vaccination before an unsolicited AE is derived from the start date of the unsolicited AE provided in the CRF and is calculated as follows:

- If an unsolicited AE has a complete start date and different to any of the vaccination dates, the start date is used to determine the last vaccination before the unsolicited AE
- If the start date is missing or partially missing, or equal to any vaccination date, then the visit number in the “Appeared after Visit” or similar field, is used to determine the last vaccination before the unsolicited AE.

4.4.1.2.4 Time of Onset

Time of onset is derived from the start date of the unsolicited AE and the date of last vaccination as described in [Section 4.4.1.2.3](#):

Time of Onset = start date of the unsolicited AE - date of last vaccination before the unsolicited AE.

The time of onset is considered as missing only if one or both dates are missing or partially missing.

The unsolicited AEs will be analyzed “Within 30 days” after each vaccination, which corresponds to AEs with a time of onset between Day 0 and Day 30.

Unsolicited AE that occurred before vaccination (negative time of onset) will not be included in analysis but will be listed separately.

Unsolicited AE which is non-serious, non-AESI and non-MAAE that occurred with a time of onset higher than defined above will not be included in analysis but will be listed separately.

- For unsolicited AE with missing day, month and year, the unsolicited AE will be classified as “Within 30 days”
- For unsolicited AE with partially missing start date, the partial available information will be used to determine if this AE is classified “Within 30 days” or “Not within 30 days”. An AE will be categorized as “Not within 30 days” only if there is clear evidence from the partially missing start date that this AE happens before the first vaccination or after the last vaccination + 30 days. In all other situations, this AE is considered as “Within 30 days”. Situations may happen as:
 - If the start date of AE has missing Day and non-missing Month and Year
 - If the “Month/Year of AE start date” < “Month/Year of first vaccination date”, then it is clear that this unsolicited AE happened before the first vaccination and this unsolicited AE will not be included in the analysis but will be listed separately.

- Else if the “Month/Year of last vaccination date” <= “Month/Year of AE start date” <= “Month/Year of (last vaccination date + 30 days)”, then this unsolicited AE will be categorized as “Within 30 days”.
- Else if the “Month/Year of AE start date” > “Month/Year of (last vaccination date + 30 days)”, then this unsolicited AE will be categorized as “not within 30 days”. If the AE is non-serious, non-AESI and non-MAAE, then it will not be included in the analysis but will be listed separately.
- If the start date of AE has missing Day and Month and non-missing Year:
 - If the “Year of AE start date” < “Year of first vaccination date”, then it is clear that this unsolicited AE happens before the first vaccination and this unsolicited AE will not be included in the analysis but will be listed separately.
 - Else if the “Year of last vaccination date” <= “Year of AE start date” <= “Year of (last vaccination date + 30 days)”, then this unsolicited AE will be categorized as “Within 30 days”.
 - Else if the “Year of AE start date” > “Year of (last vaccination date + 30 days)”, then this unsolicited AE will be categorized as “not within 30 days”. If the AE is non-serious, non-AESI and non-MAAE, then it will not be included in the analysis but will be listed separately.

A few examples of missing time of onset with start date of AE partially missing:

First injection date	Last injection date	Start date of the AE	Injection date + 30	Will be analyzed “Within 30 days” ?
16Oct2023	16Oct2023	Missing	N/A	Y
16Oct2023	16Oct2023	Sep2023	N/A	N
16Oct2023	16Oct2023	Oct2023	15Nov2023	Y
16Oct2023	16Oct2023	Nov2023	15Nov2023	Y
16Oct2023	16Oct2023	Dec2023	15Nov2023	N
05Jan2023	05Jan2023	2022	N/A	N
16Oct2023	16Oct2023	2023	15Nov2023	Y
08Dec2023	08Dec2023	2024	07Jan2024	Y
16Oct2023	16Oct2023	2024	15Nov2023	N

Time of onset period is displayed as D0-D3, D4-D7, D8-D14, D15 or later, and Missing.

4.4.1.2.5 Duration

Duration is derived from the start and end dates of the unsolicited AE:

- Duration = End date of unsolicited AE - start date of unsolicited AE + 1.

The duration is considered as missing only if one or both of the start and end dates of the unsolicited AE is missing or partially missing.

4.4.1.2.6 Serious Adverse Events

An event will be considered as a serious event if “Yes” is checked for “Serious” in the CRF.

SAEs will be analyzed throughout the study using the following periods:

- Within 7 days
- Within 30 days
- During the study (ie, all SAEs occurred during the study)
- From D31 after vaccination injection to next visit (for SAE overview only)

4.4.1.2.7 Adverse Events of Special Interest

An event will be considered as an AESI if “Yes” is checked for “Is the event an AESI?” in the CRF.

AESIs will be analyzed throughout the study using the following periods:

- Within 7 days
- Within 30 days
- During the study (ie, all AESIs occurred during the study)
- From D31 after vaccination injection to next visit (for SAE overview only)

4.4.1.3 Other Safety Endpoints

4.4.1.3.1 Action Taken

This information will be summarized as collected, including missing observations. No derivation or imputation will be done.

4.4.1.3.2 Seriousness

This information will be summarized as collected. No derivation or imputation will be done.

4.4.1.3.3 Outcome

This information will be summarized as collected. No derivation or imputation will be done.

4.4.1.3.4 Causal Relationship

There are three original relationship terms collected in this study indicating if there is a causal relationship between one AE and study vaccines or study procedures (SAEs only). It includes “relationship to investigational product (IMP)” which refers to the relationship with MenACYW or Nimenrix®, “relationship to non-investigational product (non-IMP)” which refers to the relationship with routine vaccines from the study (only collected for unsolicited injection site reactions), and “relationship to study procedures” which is applicable for SAEs only.

The information will be summarized as collected in those fields.

Missing causal relationship will be handled as described in [Section 5.3.1.2](#). Relationship to study procedure is only presented in the listing.

4.4.1.3.5 Adverse Events Leading to Study Discontinuation

This information will be summarized as collected. A flag is available in the clinical database for all AEs in order to identify AEs leading to discontinuation before the end of active phase.

In general, the items that are counted are:

- Disposition table: A participant who, on the “Completion at End of Study” form question “What was the participant's status?” has “Adverse Event” checked.
- Safety overview table: A participant who has either on the “Completion at End of Study” form, question “What was the participant's status?” has “Adverse Event” checked or lists a solicited AE that has “Caused Study Termination” checked that is at least Grade 1 or an unsolicited AE that has “Caused Study Discontinuation” checked that is at least Grade 1 or missing and is within the time period indicated.
- System Organ Class (SOC)/Preferred Term (PT) table: A solicited AE that has “Caused Study Termination” checked that is at least Grade 1 or an unsolicited AE that has “Caused Study Discontinuation” checked that is at least Grade 1 or missing and is within the time period indicated.

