Medical history	X								
Physical examination (including temperature)‡§	X						X		
Temperature measurement§			X						
Contact interactive response technology (IRT) system for vaccine group randomization	X		X				X		
Review of temporary contraindications for blood sampling**	X				X		X		X
Blood sampling (BL)††	BL0001 (2 or 3 mL)‡‡				BL0002 (3 or 4 mL)‡‡		BL0003 (5 or 6 mL)‡‡		BL0004 (5 or 6 mL)
Review warnings and precautions to vaccinations	X		X				X		
Review of contraindications to subsequent vaccinations			X				X		

Visit/Contact	Visit 1	Telephone Call (TC) 1	Visit 2	TC2	Visit 3	TC3	Visit 4	TC4	Visit 5
Age of Subject	2 months (42 to 89 days)						12-18 months*		
Study timelines (days)	Day 0	Visit 1 + 8 days	Visit 1 + 60 days	Visit 2 + 8 days	Visit 2 + 30 days	Visit 3 + 5 months AND Visit 4 – at least 14 days†	Visit 2 + at least 180 days	Visit 4 + 8 days	Visit 4 + 30 days
Time windows (days)		+2 days	+14 days	+2 days	+21 days			+2 days	+21 days
Vaccination with MenACYW conjugate vaccine or Nimenrix®	X		X				X		
Vaccination with routine pediatric vaccines§§	X		X				X		
Immediate surveillance (30 minutes)	X		X				X		
Diary card (DC) provided	DC1		DC2		DC3		DC4		
Telephone call		X***		X***		X†††		X***	
Diary card reviewed and collected			DC1		DC2		DC3		DC4
Recording of solicited injection site and systemic reactions‡‡‡	X		X§§§		X§§§				X§§§
Recording of unsolicited adverse events (AEs)						Day 0 to Day 30 after each vaccination visit			
Reporting of serious adverse events (SAEs, including adverse events of special interest [AESIs]****)						To be reported throughout the study period			
Collection of reportable concomitant medications	X		X		X		X		X
Study termination record (Completion at End of study)									X

* Visit 4 may occur anytime from the day the subject turns 12 months to the day before the subject turns 19 months of age as long as there is an interval of at least 180 days since Visit 2.

† Staff will contact subjects' parent / legally acceptable representative by telephone 5 months after the last visit in infancy and at least 14 days before Visit 4.

‡ Physical examination should be performed as per standard of care. If a routine examination had been performed within the last week by the Investigator, a sub-investigator, or a licensed nurse practitioner, it does not need to be repeated unless there were some changes in health status, in which case it may be limited to the affected area.

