5.1.5.2 Safety

Safety results will be described for subjects in all study groups after any and each vaccination at 2, 4, 6 (only for Group 4) and 12 to 18 months of age (Visits 1, 2, and 4 for Groups 1, 2 and 3, and Visits 1, 2, 3 and 5 for Group 4). The main parameters for the safety endpoints will be described by 95% CI using the exact binomial method (Clopper-Pearson method).

At least the following parameters will be presented:

- Unsolicited systemic AEs reported in the 30 minutes after each vaccination, including occurrence, nature (Medical Dictionary for Regulatory Activities [MedDRA] preferred term), duration, intensity, action taken, relationship to the product administered, and whether the event caused termination from the study.
- Solicited (prelisted in the subject's diary card and CRB) injection site and systemic reactions starting any time from Day 0 (day of vaccination) through Day 7 after each vaccination,

including occurrence, time of onset, number of days of occurrence, intensity, action taken, and whether the reaction caused termination from the study.

- Unsolicited non-serious AEs reported up to 30 days after each vaccination, including occurrence, nature (MedDRA preferred term), time of onset, duration, intensity, action taken, relationship to the product administered, and whether the event caused termination from the study.
- SAEs (including AESIs) reported throughout the study, ie, from Visit 1 (first vaccination) to the last study visit (Visit 5 for Groups 1, 2, and 3 and Visit 6 for Group 4, occurring 30 days [+21 days] after the last vaccination), including occurrence, nature (MedDRA preferred term), time of onset, duration, intensity, action taken, relationship to the product administered, whether the event caused termination from the study, outcome, elapsed time from last administration (if less than 24 hours), relationship to study procedures, and seriousness criterion.

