Safety overview after any vaccine injections – Overall Safety Analysis Set

Safety overview after vaccine injections at 2 months of age – Safety Analysis Set 1

Safety overview after vaccine injections at 4 months of age – Safety Analysis Set 2

Safety overview after vaccine injection at 6 months of age – Safety Analysis Set 3

Safety overview after vaccine injections at 12 through 18 months of age – Safety Analysis Set 4

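### In the safety-overview rule, the end-of-study-form route has no dose or period link, so an AE withdrawal can be counted in the overview of each dose the child received

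*SAP*

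**What the plan says.** SAP 4.4.1.3.5 defines AE discontinuation for three displays.

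- **Disposition table:** the end-of-study form alone.
- **Safety overview:** any of three routes. The first is the form: "Safety overview table: A participant who has either on the “Completion at End of Study” form, question “What was the participant's status?” has “Adverse Event" ticked. The second is a solicited reaction of at least Grade 1 recorded as ending participation. The third is an unsolicited AE recorded as causing discontinuation, "checked that is at least Grade 1 or missing and is within the time period indicated".
- **SOC/PT table:** AE records only, with no form route.

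The same section says that "A flag is available in the clinical database for all AEs in order to identify AEs leading to discontinuation", so event-level information exists.

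On table structure, SAP 5.1.5.2 states: "Safety results will be described for subjects in all study groups after any and each vaccination". SAP 5.1.6.1 names one overview per dose, for example "Safety overview after vaccine injections at 2 months of age – Safety Analysis Set 1", with parallel titles for SafAS2 to SafAS4 and one for any dose. Under SAP 5.2.3.2 to 5.2.3.5, each dose-specific set admits only children vaccinated at the visit concerned.

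For unsolicited AEs, SAP 4.4.1.2.3 assigns each event to its last vaccination and 4.4.1.2.4 sets a Day 0 to Day 30 window. SAP 4.4.1.2.6 and 4.4.1.2.7 add longer periods for SAEs and AESIs, including one from D31 to the next visit.

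**The concern.** The form records why a child left the study, once, at the end (SAP Table 3.3). The overview is laid out by dose. Without a rule joining the two, a status of *Adverse Event* applies in every dose-specific set that contains the child. A withdrawal that followed the toddler dose would then also be shown as an AE discontinuation after the 2-month and 4-month doses.

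Whether an event ended participation is a listed attribute of the safety endpoints (SAP 4.3.2.2). A reader of the 2-month overview would take its discontinuation count as information about the first dose. The SOC/PT table, which should itemise those events, uses a different rule and would not show the same children.

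**Working it through.** No figure in the plan bears on this point, so the check is an enumeration under the rule as written.

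**Inputs.** Per-dose overviews: SafAS1, SafAS2 and SafAS4 for Groups 1 to 3; SafAS1 to SafAS4 for Group 4 (SAP 5.2.3.2 to 5.2.3.5). Form route: true or false per child, with no further condition (SAP 4.4.1.3.5). Assumption: doses are received in order, with some safety data after each.

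**Formula.** A child who received k doses is in k dose-specific sets. If the form says *Adverse Event*, the form route therefore counts the child in k per-dose overviews. The event follows one last dose, so k − 1 of these counts are repeats.

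| Last dose received | Groups 1 to 3: overviews (repeats) | Group 4: overviews (repeats) |
|---|---|---|
| Dose 1 | 1 (0) | 1 (0) |
| Dose 2 | 2 (1) | 2 (1) |
| Dose 3 | 3 (2) | 3 (2) |
| Dose 4 | not applicable | 4 (3) |

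The any-dose overview counts each child once in every case.

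**Example 1.** A Group 1 child has an AE starting 10 days after the Visit 4 dose and is withdrawn for it. The child is in SafAS1, SafAS2 and SafAS4, so the form route gives three counts. The last-vaccination rule would place the event in the 12-to-18-month overview only.

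**Example 2.** A Group 1 child has an SAE starting 5 months after dose 2, before the toddler dose, and is withdrawn. The child is in SafAS1 and SafAS2, so the form route gives two counts. By last vaccination the event belongs after dose 2, in a period later than Day 30. The 2-month count is therefore a repeat. The 4-month count is correct only in a row whose period extends past Day 30; the form route would also admit it to a 30-day row.

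**If the period condition covers all three routes.** The condition needs an onset date or a dose, and 4.4.1.3.5 gives neither for the form. SAP 4.4.4.3 uses a termination date to compute participation time, but no sentence brings it into this rule, and a leaving date is not an onset date.

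**Overview against SOC/PT.** A child with *Adverse Event* on the form and no flagged AE enters the overview but not the SOC/PT table. Such cases are plausible: Protocol 5.2.9 has a voluntary withdrawal for safety concerns recorded under that reason, and 5.2.11 extends the category to definitive contraindications that are AEs or SAEs.

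**The case against.** The strongest reply is that the text is loose rather than wrong. The period condition closes one sentence listing three alternatives and may be meant to govern all of them; the list is introduced as a general description; and the per-dose overview titles appear only under the COVID-19 outputs, which depend on more than 10% of subjects being impacted. No table shell shows the form-based row in each per-dose overview. This stands in part: duplication follows from the rule as written, but it may not be intended. It does not remove the need for a change, because the alternative reading cannot be programmed without an unwritten decision, and the commitment in 5.1.5.2 to results after each vaccination is unconditional.

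A reader might infer three stronger things that the documents do not support.

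- **Every withdrawal appears in every per-dose overview.** It does not, because SafAS2 to SafAS4 exclude children not vaccinated at those visits.
- **A late withdrawal is misplaced after dose 2 as well as after dose 1.** For SAEs and AESIs the D31-to-next-visit period offers a place after dose 2, provided the next visit is taken as the next vaccination visit (Visit 3 in Groups 1 to 3 is itself only 30 to 51 days after Visit 2). Non-serious events are recorded only to Day 30 or the next visit (SAP 4.3.2.3.3), so late cases would be mainly SAEs.
- **A typical inflation factor can be quoted.** The documents give neither an expected number of AE withdrawals nor their timing, so only the per-child maximum can be stated.

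**Conclusion.** The point holds as a drafting gap with a definite consequence if applied literally. One AE withdrawal after dose k is counted in k per-dose overviews: at most 3 in Groups 1 to 3 and 4 in Group 4, against one that it belongs to. There is no repeat after dose 1 and none in the any-dose overview. This rests on the form route having no period condition and on the overview row being produced per dose; on the other reading of the period condition, the form route is undefined rather than duplicated.

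The priority is low. The row is descriptive, the same rule applies in all groups, the disposition table counts each child once, and the SOC/PT table uses AE-level timing. The primary and secondary non-inferiority analyses are untouched.

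**What to change.** Amend SAP 4.4.1.3.5 as follows.

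1. Use the end-of-study form only in the disposition table and in the any-dose, during-the-study overview.
2. In per-dose overviews, count children with a solicited or unsolicited AE flagged as causing discontinuation. Assign the event to its last vaccination (4.4.1.2.3 for unsolicited AEs; the vaccination it was solicited after for solicited reactions) and to the period of the row, including D31 to next visit for SAEs and AESIs.
3. List children with *Adverse Event* on the form but no flagged AE. They remain in the any-dose overview and absent from the SOC/PT table, so the listing is what reconciles the two.

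The cost is a short SAP edit, a small programming change and one listing. The discontinuation flag already exists, so no data collection is needed. Per-dose counts will fall or stay the same.

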4.3.2.2 Safety Endpoints

The following endpoints will be used for all subjects for the evaluation of safety:

- Unsolicited systemic AEs reported in the 30 minutes after each vaccination, including occurrence, nature (Medical Dictionary for Regulatory Activities [MedDRA] preferred term), duration, intensity, action taken, relationship to the product administered, and whether the event caused termination from the study.
- Solicited (prelisted in the subject's diary card and CRB) injection site and systemic reactions starting any time from Day 0 (day of vaccination) through Day 7 after each vaccination, including occurrence, time of onset, number of days of occurrence, intensity, action taken, and whether the reaction caused termination from the study.
- Unsolicited non-serious AEs reported up to 30 days after each vaccination, including occurrence, nature (MedDRA preferred term), time of onset, duration, intensity, action taken, relationship to the product administered, and whether the event caused termination from the study.

- SAEs (including AESIs) reported throughout the study, ie, from Visit 1 (first vaccination) to the last study visit (Visit 5 for Groups 1, 2, and 3 and Visit 6 for Group 4, occurring 30 days [+21 days] after the last vaccination), including occurrence, nature (MedDRA preferred term), time of onset, duration, intensity, action taken, relationship to the product administered, whether the event caused termination from the study, outcome, elapsed time from last administration (if less than 24 hours), relationship to study procedures, and seriousness criterion.

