4.4 Derived Endpoints: Calculation Methods

4.4.1 Safety

4.4.1.1 Solicited Reactions

4.4.1.1.1 Daily Intensity

All daily records for solicited reactions will be derived into daily intensity according to the following classification: None, Grade 1, Grade 2, Grade 3, or Missing (Unknown).

For the derivation of daily intensities, the following sequential steps will be applied:

- 1) Solicited reactions (except Fever/Pyrexia) with CRF presence recorded as “No” and with all daily records missing (Unknown) then all daily intensities will be derived as None.

- 2) For non-measurable solicited reactions, daily intensities will correspond to daily records reported in the clinical database. For measurable solicited reactions the daily measurements reported in the clinical database will be converted based upon the intensity scales defined in the protocol; this assumes a reaction that is too large to measure (non-measurable, “NM”) is Grade 3. Note the intensity could be considered “None” (not a reaction) in the analysis despite being considered a reaction by the investigator .

Note: The maximum intensity on the ongoing period is derived from the record of the maximum intensity/measurement after the end of the solicited period following the rule described above.

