4.4.1.1.2 Maximum Overall Intensity

Maximum overall intensity is derived from the daily intensities computed as described in [Section 4.4.1.1.1](#) and is calculated as the maximum of the daily intensities over the period considered.

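### A solicited reaction flagged as ending participation is left out of the SOC/PT discontinuation table when its grade is missing, although an ungraded unsolicited event is counted (minor)

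*SAP*

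**What the plan says.** SAP 4.4.1.3.5 opens with "This information will be summarized as collected" and then says what is counted, in general, in three places.

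- **Disposition table:** participants whose end-of-study form has Adverse Event as the status.
- **Safety overview table:** the bullet begins "Safety overview table: A participant who has either on the" end-of-study form. It counts a child through that status or through a flagged event.
- **SOC/PT table:** flagged events only.

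The overview and SOC/PT bullets word the event condition alike. For a solicited reaction with the termination flag, the condition is "checked that is at least Grade 1 or an unsolicited AE that has" the discontinuation flag. For the unsolicited event the sentence continues "checked that is at least Grade 1 or missing and is within the time period indicated". The allowance for a missing grade stands only in the second clause.

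SAP 4.3.2.2 makes termination part of the solicited-reaction endpoint, which includes "intensity, action taken, and whether the reaction caused termination from the study".

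**The concern.** The grade condition is written out separately for each type of event, so the allowance for a missing grade cannot be read back onto solicited reactions. The SAP gives no reason for the difference. A site may record that a solicited reaction ended a child's participation and yet have no grade or measurement for it. The stated rule then drops that reaction from the one discontinuation table that names the event.

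This fits poorly with the section's own promise to summarise the information as collected. It also departs from how the SAP treats other gaps in safety data. A missing relationship for an unsolicited systemic event is taken as related (5.3.1.2). An unsolicited event with a wholly missing start date is placed within 30 days (4.4.1.2.4). A reaction too large to measure becomes Grade 3 (4.4.1.1.1). At stake is the completeness of a descriptive table for a stated safety endpoint, and whether its counts can be traced to the overview.

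**Working it through.** The plan states no figure to reproduce and no formula applies. The check takes the SOC/PT rule case by case, then asks whether the critical case can arise.

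**Step 1: the rule, with the site's flag checked.**

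| Derived grade | Solicited reaction | Unsolicited event within the period |
|---|---|---|
| Grade 1, 2 or 3 | counted | counted |
| Missing | **not counted** | counted |
| None / Grade 0 | not counted | not counted |

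The two columns differ only in the Missing row.

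**Step 2: can a flagged solicited reaction have a missing grade?**

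- SAP 4.4.1.1.1 derives daily intensity "according to the following classification: None, Grade 1, Grade 2, Grade 3, or Missing (Unknown"), so Missing is a permitted result.
- The only rule there that resolves wholly missing daily records requires CRF presence recorded as No, and it excludes fever. It reads "and with all daily records missing (Unknown) then all daily intensities will be derived as None". A reaction recorded as present with no daily grade stays Missing. (None would fail the Grade 1 condition anyway.)
- SAP 4.4.1.1.3 turns a missing intensity into a missing presence and drops the child from the analysis of that endpoint.
- SAP 5.3.1.3 refers missing solicited intensities back to 4.4.1.1.1 and adds nothing.

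The case can arise, and no other rule brings the reaction back.

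**Step 3: how narrow is it?** I assume that the grade meant in 4.4.1.3.5 is the maximum overall intensity of 4.4.1.1.2, which "is calculated as the maximum of the daily intensities over the period considered". One day at Grade 1 or more is then enough for the reaction to count. If missing days are ignored in that maximum, which the SAP does not say, a reaction with some days at None and the rest missing derives to None and belongs in the last row of the table.

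**Step 4: where does the child still appear?**

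- End-of-study status Adverse Event: counted in disposition and overview, but the reaction is absent from SOC/PT.
- Any other status: not counted under Adverse Event in disposition, and this reaction does not bring the child into the overview, because its event route carries the same grade condition.

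Protocol 5.2.11 asks for the most significant reason and ranks Adverse Event first, so the first situation should be the usual one.

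**Step 5: direction.** Each affected reaction removes one event from its preferred-term row. Nothing in the rule adds one, so the omission can only lower the solicited count.

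**The case against.** The strongest reply is that the two kinds of event are defined differently. An unsolicited event exists once it has a verbatim term and is not Grade 0 (SAP 4.4.1.2.1), so a missing grade still leaves an event. Solicited reactions are prelisted and their presence is derived only from intensity (4.4.1.1.3), so a missing grade leaves presence unknown. On this view 4.4.1.3.5 simply applies that definition. This explains the asymmetry but does not remove the gap. In this table the site's termination flag already restricts the count, so admitting a missing grade adds only reactions that the site positively recorded, not empty diary rows. What stands is that the SOC/PT table would then count a reaction that the solicited-reaction tables treat as presence missing, and this needs a footnote.

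Three stronger readings are tempting, and the documents do not support them.

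- *A reader might infer that families who leave because of a reaction are the least likely to return a completed diary, so missing grades would concentrate here.* The documents do not say so, and they provide for recovering the data. Events that caused discontinuation are followed until resolved, stable or chronic unless contact is refused (Protocol 5.1.4). Sites contact children terminated because of an AE (5.2.12). Information not in the diary is captured in source documents (11.1), and diary gaps are clarified verbally (13.2).
- *A reader might infer a material undercount, or that the child vanishes from the safety reporting.* No expected number is given, so no percentage can be justified. The child stays in two tables if the end-of-study status is Adverse Event, and subject listings show missing data as missing (SAP 5.3.1).
- *A reader might infer that the missing words alone explain any disagreement between the tables.* They do not. The counts can also differ when the form says Adverse Event but no event is flagged, when a flagged measurement derives to None, or when a flagged unsolicited event falls outside the period.

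**Conclusion.** The gap is real and minor. As written, a solicited reaction that the site flagged as ending participation, with no grade on any day, is left out of the SOC/PT discontinuation table and fails the event route of the overview. An unsolicited event in the same position is counted in both.

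No numerical size can be given. The case should be rare, and safety is descriptive, so no hypothesis, alpha or power is touched. The conclusion rests on the literal wording of the two bullets and on the grade there being the derived maximum overall intensity. The bullets are introduced as a general description, so the programmed table might be more inclusive, but the SAP does not say that it is.

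**What to change.** In the overview and SOC/PT bullets of SAP 4.4.1.3.5, extend the solicited clause to admit a missing grade, in the same words as the unsolicited clause. Add a footnote that such reactions remain presence-missing in the solicited-reaction tables under 4.4.1.1.3. List any flagged reaction that derives to None, so that the SOC/PT and overview counts can be reconciled. Reactions deriving to None stay out of the counts, in line with Grade 0 unsolicited events.

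The cost is two words in each of two bullets, one programming condition, one footnote and a short listing, with no new data. The downside is a small, footnoted difference from the solicited-reaction tables. The change does not by itself make the SOC/PT and overview counts equal. The listing makes the None cases traceable, and the differences from unflagged or out-of-period events remain.
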